Healthy male and female (of non-childbearing potential) volunteers aged 18 to 45 years (inclusive) who are non-smokers, have a body mass index (BMI) between 18 and 30 kg/m² (inclusive) and weigh at least 50 kg and no more than 100 kg (inclusive), have a calculated creatinine clearance greater than 50 mL/min using the Cockcroft-Gault formula. Healthy volunteers with current or past history of central serous retinopathy or retinal vein thrombosis, intra-ocular pressure greater than 21 mmHg or uncontrolled glaucoma will be excluded.

Investigational product, dosage and mode of administration

A single administration of 75 mg selumetinib will be administered as 3 x 25 mg oral capsules (Treatment A).

Comparator, dosage and mode of administration

Healthy volunteers will receive single daily oral doses of 600 mg (2 x 300 mg) rifampicin on Days 4 to 11 and Days 13 to 14 (Treatment B). On Day 12, the volunteers will receive 600 mg (2 x 300 mg) rifampicin and 75 mg (3 x 25 mg) selumetinib at the same time (Treatment C).

Duration of treatment

Volunteers will participate in the study for approximately 8 weeks; including screening over 28 days. Volunteers will be resident in the study center from Day -1 until all study assessments are completed on Day 15, with a follow-up visit 7 to 10 days after discharge (Day 15).

Outcome variable(s):

- Pharmacokinetics

The primary PK parameters will be: maximum observed plasma concentration (C_{max}), area under the plasma concentration-time curve from time zero to infinity (AUC), and area under plasma concentration-time curve to time of last measurable concentration ($AUC_{(0-t)}$).

The secondary PK parameters will be: time to reach maximum observed concentration administration (t_{max}), area under the plasma concentration time curve from zero to 12 hours post-dose ($AUC_{(0-12)}$), terminal rate constant (λ_z), terminal elimination half-life ($t_{1/2}$), apparent oral clearance (CL/F), apparent volume of distribution at steady state (V_{ss}/F), apparent volume of distribution during the terminal phase (V_z/F), and mean residence time (MRT) for selumetinib, and AUC, C_{max} , t_{max} , $t_{1/2}$, λ_z , AUC_{0-12} , $AUC_{(0-t)}$, and the metabolite to parent AUC and C_{max} ratios (MR_{AUC} and $MR_{C_{max}}$) for N-desmethyl selumetinib.

Pharmacokinetic parameters will not be determined for rifampicin. Only the 2 hours post-dose plasma concentrations will be reported.

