1.2 Rationale for conducting this study

As selumetinib is metabolized by cytochrome P450 (CYP)3A4, it is important to understand whether the inhibition or induction of CYP3A4 influences selumetinib exposure. This study is designed to investigate the effect of co-administration of the potent CYP3A4 inducer rifampicin with selumetinib, as significant induction of CYP3A4 could potentially reduce selumetinib exposure, thus reducing efficacy.

The primary objective of this study is to assess any differences in the pharmacokinetics (PK) of selumetinib at a dose of 75 mg when administered with or without rifampicin.

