Inclusion/exclusion criteria	X	X									
Weight	X	X									X
Height	X										
Residency period		X	X	X	X	X	X	X	X	X ^b	
Administration of selumetinib			X					X			
Administration of rifampicin					X	X	X	X	X		
Vital signs ^c	X		X ^c	X	X			X ^c	X		X
12-lead ECG	X ^d		X ^e					X ^e			X
Hematology, clinical chemistry, urinalysis ^f	X	X			X ^f	X		X ^f		X	X
Drugs of abuse screen ^g	X	X									

Table 2 Study plan

Days	Visit 1			Visit 2					Visit 3		
	Screening	Treatment A (selumetinib only)		Treatment B (rifampicin only)			Treatment C (selumetinib +rifampicin)		Discharge	Follow-up visit	
	-28 to -2	-1	1	2 to 3	4	5 to 10	11	12	13 to 14	15	7 to 10 days after discharge
Ophthalmic examination ^a	X	X									
Physical examination ^h	X	X								X	X
Selumetinib PK blood ⁱ			X	X	X ^m			X	X	X	
Rifampicin PK blood ^l						X ^l			X		
4β-hydroxycholesterol and cholesterol blood ^k					X			X	X		
Optional pharmacogenetic blood ^j		X									
Pregnancy test (female subjects only)	X	X									X
Follicle-stimulating hormone ⁿ	X										
AEs		X	X	X	X	X	X	X	X	X	X
SAE	X	X	X	X	X	X	X	X	X	X	X
Concomitant medication	X	X	X	X	X	X	X	X	X	X	X

AE: Adverse event, ECG: Electrocardiogram, PK: Pharmacokinetic, IOP: Intra-ocular pressure, SAE: Serious adverse event

- a Ophthalmic examination (best corrected visual acuity, IOP, slit-lamp fundoscopy) will be conducted at screening or Day -1 (considered as the baseline value; no need to repeat) and for cause (on occurrence of an AE only).
- b Volunteers will be discharged from the study center on the morning of Day 15 following completion of all the study assessments scheduled for that day.
- c Vital signs includes supine blood pressure and heart rate to be measured after the volunteer has been resting for 10 minutes and before any blood sampling. On the selumetinib administration days of each treatment period, blood pressure and pulse rate will be recorded at pre-dose, 1.5 hours (t_{max}), 4 hours, 8 hours, 12 hours, and 24 hours post-dose.

- d 12-lead ECGs. Patients should be supine and resting for at least 10 minutes before the ECG recording. If the volunteer has QTcF ≥ 450 ms on baseline ECG, the ECG may be repeated (at least 24 hours apart). The average QTcF from the 2 screening ECGs must be less than ≥ 450 ms in order for the volunteer to be eligible for the study.

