5.5.2 Doses and treatment regimens

The dose level of 75 mg of selumetinib (3 x 25 mg capsules) is considered to be in the therapeutic dose range and is the maximum dose permitted in healthy volunteers. A dose of 75 mg twice daily is being investigated in ongoing efficacy studies of selumetinib.

Daily administrations of 600 mg (2 x 300 mg) rifampicin oral capsules for 9 days will maximize the induction effect on CYP3A4.

Treatment A (selumetinib alone):

A single administration of 75 mg selumetinib will be administered as 3 x 25 mg oral capsules in the fasted state. Healthy volunteers will be fasted overnight for at least 10 hours before receiving selumetinib and until 4 hours post-dose. No fluids will be allowed from 1 hour before investigational product administration until 1 hour after investigational product administration, except for water needed to swallow the investigational product. Standardized meals (lunch, dinner, and a snack) will be provided at the same time during Visit 2.

Treatment B (rifampicin):

Healthy volunteers will receive single daily oral doses of 600 mg (2 x 300 mg) rifampicin as capsules on Days 4 to 11 under food restriction where they will be fasted overnight for at least 10 hours before receiving rifampicin and until 1 hour post-dose. Standardized meals (lunch, dinner, and a snack) will be provided at the same time during Visit 2. No fluids will be allowed from 1 hour before investigational product administration until 1 hour after investigational product administration, except for water needed to swallow the investigational product.

Treatment C (rifampicin + selumetinib):

On Day 12, healthy volunteers will receive 600 mg (2 x 300 mg) rifampicin oral capsules and 75 mg (3 x 25 mg) selumetinib oral capsules in the fasted state (fasted from midnight on Day 11 to 4 hours after investigational product administration) administered at the same time. Healthy volunteers will continue to receive single daily oral 600 mg (2 x 300 mg) doses of rifampicin on Days 13 to 14 under food restriction where they will be fasted overnight for at least 10 hours before receiving rifampicin and until 1 hour post-dose. Standardized meals (lunch, dinner, and a snack) will be provided at the same time during Visit 2. No fluids will be allowed from 1 hour before investigational product administration until 1 hour after investigational product administration, except for water needed to swallow the investigational product.

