11.2 Calculation or derivation of pharmacokinetic variables

11.2.1 Selumetinib and metabolites

Pharmacokinetic parameters will be determined by using standard non-compartmental methods with Phoenix[®] WinNonlin Professional Version 6.3 or higher) or SAS[®] Version 9.2 or higher). Standard Operation

Procedures and Work Instructions will be used as the default methodology, unless otherwise specified. Actual elapsed time from investigational product administration will be used for final PK parameter calculations. Pharmacokinetic parameter units will be consistent with the concentration units specified in the bioanalytical data.

The following PK parameters will be determined for plasma selumetinib and N-desmethyl selumetinib (and the amide metabolite, if deemed appropriate):

AUC Area under the plasma concentration-time curve from time zero to infinity, calculated by linear up/log down trapezoidal summation.

AUC_(0-t) Area under the plasma concentration-time from time zero to the time of the last quantifiable concentration, calculated by linear up/log down trapezoidal summation.

$AUC_{(0-12)}$	Area under the plasma concentration-time curve from time zero to 12 hours post-dose, calculated by linear up/log down trapezoidal summation.
C_{max}	Maximum concentration, obtained directly from the observed concentration versus time data.
t_{max}	Time to C_{max} .
CL/F	Apparent systemic plasma clearance (selumetinib only).
V_{ss}/F	Apparent volume at distribution equilibrium, mean residence time (MRT)*CL/F (selumetinib only).
V_z/F	Apparent volume at distribution (selumetinib only).
$t_{1/2}$	Terminal half-life.
λ_z	Terminal rate constant.
MR_{AUC}	AUC metabolite to parent ratio, N-desmethyl selumetinib AUC/selumetinib AUC.
$MR_{C_{max}}$	C_{max} metabolite to parent ratio, N-desmethyl selumetinib C_{max} /selumetinib C_{max} .
MRT	Mean residence time.

No dose adjustment is required for PK parameters which require selumetinib dose for calculation since the selumetinib dose being administered is based on the free base equivalent.

The following PK parameters for plasma selumetinib and N-desmethyl selumetinib (and the amide metabolite, if deemed appropriate) will be calculated for diagnostic purposes and listed, but will not be summarized:

$t_{1/2}$, Interval	The time interval of the log-linear regression to determine λ_z .

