12.3 Determination of sample size

The primary objective of this study is to investigate the effect of multiple 600 mg (2 x 300 mg) oral doses of rifampicin on the exposure of a single 75 mg oral dose of selumetinib in healthy volunteers by comparing AUC and C_{max} of selumetinib in the presence and absence of rifampicin.

A sample size of 20 evaluable healthy volunteers has been selected based on the desire to gain adequate information while exposing as few healthy volunteers as possible to study procedures. Twenty-four healthy volunteers will be enrolled into the study in order to have at least 20 evaluable healthy volunteers complete the study (allowing for an approximate 20% dropout rate).

Table 6 displays expected 90% CI for a range of possible drug-drug interaction effects at the selected sample size of 20 evaluable volunteers. Within-volunteer estimates of coefficient of variation (CV) (16.9% for AUC and 34.0% for C_{max}) observed in a prior clinical study (Study D1532C00066) were used in these calculations. These 90% CIs demonstrate that good precision of the drug-drug interaction effect will be achieved from a sample size of 20 evaluable healthy volunteers.

Table 6 90% Confidence intervals for C_{max} and AUC varying drug-drug interaction effects given an evaluable sample size of 20

Parameter	Drug-drug interaction effect: Relative reduction of C_{max} or AUC (geometric least squares means ratio)						
	70% (0.3)	60% (0.4)	50% (0.5)	40% (0.6)	30% (0.7)	20% (0.8)	10% (0.9)
C_{max}	0.25, 0.36	0.34, 0.48	0.42, 0.59	0.51, 0.71	0.59, 0.83	0.67, 0.95	0.76, 1.07
AUC	0.27, 0.33	0.37, 0.44	0.46, 0.55	0.55, 0.65	0.64, 0.76	0.73, 0.87	0.82, 0.98

C_{max} : maximum concentration in the sampled matrix

AUC: area under the concentration-time curve in the sampled matrix from time zero to infinity

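### Vss/F is defined as MRT × CL/F from oral data alone, so it includes absorption time, overstates the volume, and is not comparable between treatments when systemic clearance changes

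*Protocol*

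**What the plan says.** Section 11.2.1 sets the general method: "Pharmacokinetic parameters will be determined by using standard non-compartmental methods". Within that list, Vss/F is defined as "Apparent volume at distribution equilibrium, mean residence time (MRT)*CL/F (selumetinib only". MRT is listed without a formula, and no mean absorption or input time is subtracted anywhere. The synopsis lists the same quantity among the secondary PK parameters under the label "apparent volume of distribution at steady state".

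Section 5.5.2 describes Treatment A as follows: "A single administration of 75 mg selumetinib will be administered as 3 x 25 mg oral capsules in the fasted state". Treatment C on Day 12 uses the same oral capsules together with rifampicin. There is no intravenous reference.

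Section 1.2 gives the expected direction of the interaction: "significant induction of CYP3A4 could potentially reduce selumetinib exposure". Table 6 in Section 12.3 covers AUC ratios from 0.3 to 0.9. Section 12.2.3.1 summarises PK parameters by treatment and analyte. Only Cmax, AUC and AUC(0-t) enter the mixed model.

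**The concern.** After an oral dose, the non-compartmental MRT (AUMC/AUC) measures time in the body plus time spent getting in. Multiplying it by CL/F therefore yields a volume plus a term, MIT × CL/F, that is not a volume.

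In a study of one treatment this would be a roughly fixed nuisance. Here the extra term scales with CL/F, the quantity that rifampicin is expected to change, and the parameter is tabulated for the same volunteers with and without rifampicin. A reader who sees a higher Vss/F in Treatment C could take it as an effect of rifampicin on selumetinib distribution when part or all of the rise is an artefact of the formula.

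**Working it through.** **Inputs from the protocol**
- Formula: Vss/F = MRT × CL/F (Section 11.2.1).
- Route: oral in both periods (Section 5.5.2).
- AUC ratios R = C/A considered: 0.3 to 0.9 (Table 6). CL/F = dose/AUC, so these correspond to CL/F rising by a factor of 1/0.3 = 3.33 down to 1/0.9 = 1.11.
- A footnote to Table 2 places tmax at 1.5 h, so input is not instantaneous and MIT > 0.

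The protocol states no value for Vss/F, MRT or MIT, so there is no figure of its own to reproduce.

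**Assumptions (not in the protocol)**
- MRT is uncorrected AUMC/AUC, inferred from the reference to standard methods.
- MIT is 0.5–2 h and unchanged by rifampicin.
- Systemic residence time MRTsys is 6–12 h with selumetinib alone.

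**Step 1: what the formula returns.** Oral MRT = MRTsys + MIT, and true Vss/F = MRTsys × CL/F. Therefore

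MRT × CL/F = Vss/F + MIT × CL/F.

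The relative overstatement is m = MIT/MRTsys. In Treatment A it runs from 0.5/12 = 4% to 2/6 = 33%.

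**Step 2: AUC falls because systemic CL rises (F and true Vss unchanged).** MRTsys in Treatment C becomes R × MRTsys, so the overstatement becomes m/R. The apparent C/A ratio of a truly constant Vss/F is

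(1 + m/R) / (1 + m).

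| R | m = 0.0417 (MIT 0.5 h, MRTsys 12 h) | m = 0.333 (MIT 2 h, MRTsys 6 h) |
|---|---|---|
| 0.9 | 1.0463/1.0417 = 1.00 | 1.370/1.333 = 1.03 |
| 0.5 | 1.0833/1.0417 = 1.04 | 1.667/1.333 = 1.25 |
| 0.3 | 1.1389/1.0417 = 1.09 | 2.111/1.333 = 1.58 |

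**Step 3: AUC falls because F falls (CL unchanged).** MRTsys and MIT are unchanged, so the overstatement is m in both treatments. True Vss/F itself rises by 1/R. The C/A ratio is then not distorted, although the absolute excess MIT × CL/F still grows.

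**Step 4: check at the protocol's sampling times.** Noiseless two-compartment oral profiles were analysed at the 16 scheduled times with the linear-up/log-down rule. Assumed values were V1 50 L, V2 70 L (Vss 120 L), Q 8 L/h and CL 12 L/h, giving MRTsys 10 h. At MIT 1 h, the algebra gives 120 + 1 × 12 = 132 L in A and 120 + 1 × 24 = 144 L in C (CL doubled). The non-compartmental estimates were 132.7 L and 147.2 L. Agreement was within about 2% for MIT 1–2 h and 5% for MIT 0.5 h.

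**Step 5: is Vz/F a clean replacement?** Vz = CL/λz. With the same assumed parameters, λz is the smaller root of λ² − (CL/V1 + Q/V1 + Q/V2)λ + (CL/V1)(Q/V2) = 0.
- CL 12 L/h: λz = 0.0604 per h, Vz = 12/0.0604 ≈ 199 L.
- CL 24 L/h: λz = 0.0815 per h, Vz = 24/0.0815 ≈ 294 L.

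Vz rises by about 48% with no change in distribution. The size depends on the assumed compartments. Under one-compartment disposition Vz would not move.

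**The case against.** The strongest objection concerns mechanism. CL/F rises when CL rises or when F falls, and Section 1.2 does not say by which route exposure would drop. A reader might infer that Vss/F must rise spuriously whenever rifampicin raises CL/F. The protocol does not support that: under a pure fall in F, the rise in apparent volume is real and the relative bias is equal in both treatments. This part of the objection stands, and the claim about the C/A comparison is conditional on it. The overstatement within each treatment is not.

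The size is also assumed. The upper corner (MIT 2 h, MRTsys 6 h) implies tmax = ln(0.5/0.1667)/(0.5 − 0.1667) = 3.3 h under one-compartment disposition, against the 1.5 h given in Table 2. Fitting 1.5 h on that model gives MIT 0.44–0.58 h and a C/A ratio of 1.04–1.09 at R = 0.5. Two-compartment disposition can accommodate the corner, so the range is not ruled out, but its upper end should not be taken as likely.

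A reader might also infer that replacing Vss/F by Vz/F would solve the problem. It would not, as step 5 shows: Vz/F has no additive input-time term, but it also moves with clearance when disposition is multi-compartmental.

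Finally, no formal A-versus-C comparison of Vss/F is planned, no objective concerns distribution, and MRT and CL/F are reported beside it. That limits the consequence. It does not make the stated formula return the labelled quantity, and the two values will still be tabulated by treatment.

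**Conclusion.** As defined, the parameter is not the apparent steady-state volume that its label claims. It exceeds that volume by MIT × CL/F in both treatments, provided MRT is the usual uncorrected AUMC/AUC; an all-oral design offers no model-free way to correct it. Under the assumed ranges the overstatement in Treatment A is 4–33%.

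A spurious rise in Treatment C follows only to the extent that systemic clearance increases: negligible at an AUC ratio of 0.9, and potentially 9–58% at 0.3. These figures rest on an assumed MIT and residence time, and on MIT being the same in both periods.

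The point is minor. Vss/F is secondary and descriptive. The comparisons of Cmax, AUC and AUC(0-t), and the sample size, are untouched.

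**What to change.** Either of two changes is enough.

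1. Delete Vss/F from the secondary PK parameters in the synopsis and from Section 11.2.1.
2. Keep the quantity but name it oral MRT × CL/F, including absorption time, in both places. Add a statement that a difference between Treatments A and C is not evidence of a change in distribution.

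MRT and Vz/F can remain as planned. Vz/F should not be presented as a clearance-independent replacement, and the same caution belongs beside it.

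The cost is one deleted or relabelled secondary parameter and a footnote. No samples, data or planned model analyses are lost.

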11.2.2 Rifampicin

Pharmacokinetic parameters will not be derived for rifampicin. Only the 2 hours post-dose plasma concentrations will be reported and assessed.

11.2.3 4 β -hydroxycholesterol and cholesterol

The following will be calculated using 4 β -hydroxycholesterol and cholesterol assessments:

4 β -hydroxycholesterol ratio Day x The post-treatment 4 β -hydroxycholesterol ratio (4 β -hydroxycholesterol/cholesterol) on Day 12 or Day 14 compared to the pre-treatment (Day 4 pre-dose) ratio (ie, Day 12 or Day 14/Day 4).

12. STATISTICAL METHODS AND SAMPLE SIZE DETERMINATION

12.1 Description of analysis sets

12.1.1 Safety analysis set

All healthy volunteers who received at least 1 administration of investigational product (selumetinib or rifampicin) will be included in the safety population.

12.1.2 Pharmacokinetic analyses set

The PK analysis set will include all healthy volunteers who receive at least 1 administration of selumetinib and have at least 1 post-dose PK measurement without important protocol deviations/violations or events thought to significantly affect the PK of the investigational product (eg, healthy volunteer vomited at or before 2 times median t_{max} ; wrong dose administered; prohibited concomitant medication; etc). The PK scientist will evaluate the

strategy for dealing with data affected by protocol deviations before any formal statistical analysis is performed.

12.2 Methods of statistical analyses

Statistical analyses will be performed per Standard Operating Procedures using SAS[®] Version 9.2 or higher and, where appropriate, additional validated software.

A healthy volunteer who withdraws prior to the last planned observation in the study period will be included in the analyses up to the time of discontinuation. No adjustment or imputation will be utilized for missing values or for healthy volunteers who withdraw prior to completing the study, nor will analyses be restricted to healthy volunteers with complete data.

Data from non-valid healthy volunteers (healthy volunteers excluded from the analysis set[s]), which are recorded in the database, will only be presented in listings.

The analysis of data will be based on different subsets according to the purpose of analysis, ie, for safety and PK, respectively. The as-treated principle will be applied to all evaluations; ie, healthy volunteers who receive another treatment than the one assigned in the randomization list will be analyzed as belonging to the actual treatment group.

All derived variables/parameters will be rounded for reporting purposes in the summary tables and healthy volunteer listings, as per Standard Operating Procedures.

12.2.1 Subject characteristics

Continuous variables will be summarized using descriptive statistics (n, mean, standard deviation [SD], minimum, median, maximum) by treatment. Categorical variables will be summarized in frequency tables (frequency and proportion) by treatment group.

12.2.2 Safety and tolerability

All safety data (scheduled and unscheduled) will be presented in the data listings. Continuous variables will be summarized using descriptive statistics (n, mean, SD, minimum, median, maximum) by treatment. Categorical variables will be summarized in frequency tables (frequency and proportion) by treatment.

Safety variables (eg, clinical laboratory values and vital signs) will be reported to the same precision as the source data. Derived variables will be reported using similar precision to those from which they were derived.

Extra measurements (such as unscheduled or repeat assessments) will not be included in the descriptive statistics by scheduled time point, but will be included in data listings. All AEs and clinical laboratory outliers that occur following the first dose of investigational product will be included in the analyses of AEs and outlier events, including episodes that occur at unscheduled evaluations, evaluations, or during the washout period.

All available data from healthy volunteers in the safety analysis set will be included in the safety analyses.

All AEs will be collected for each healthy volunteer from Day -1 Visit 2 until the follow-up visit. All SAEs will be collected for each healthy volunteer from the time when informed consent is obtained until the follow-up visit.

Adverse events will be listed for all healthy volunteers with AEs that occur before investigational product administration indicated on the listing. The number of AEs experienced following administration of the investigational product will be summarized in tables using the Medical Dictionary for Regulatory Activities (MedDRA) (Version 13.0 or higher) System Organ Class and Preferred Term. These summary tables will also be produced with severity and causality of AEs added as additional classification factors. The number of AEs overall, SAEs, OAEs, AEs that lead to withdrawal, AEs of severe intensity, and causally-related AEs will be summarized. Any AE occurring post-dose will be considered associated with the last administration of investigational product taken. Any AE occurring on Visit 2 Day -1 will not be included in the summaries.

Tabulations and listings of data for vital signs, ECGs, and clinical laboratory tests will be presented, as appropriate. Results from physical examinations will be presented separately in listings only. All continuous safety data will be summarized across all treatments for the absolute value at each scheduled assessment and for the corresponding change-from-baseline. For clinical laboratory tests, listings of values for each healthy volunteer will be presented with abnormal or out-of-range values flagged. Clinical laboratory data will be reported in Système International units in the CSR. Additional graphical presentations of the data eg, shift plots comparing baseline to on treatment values will be generated as appropriate to aid the interpretation of safety data.

